Abbreviations and Special Terms	Definition
PET	positron emission tomography
PFS	progression-free survival
PI3K δ	phosphoinositide 3-kinase delta
PJP	Pneumocystis jiroveci pneumonia
PK	pharmacokinetic
PMD	progressive metabolic disease
PMDA	Pharmaceuticals and Medical Devices Agency
PP	per Protocol
PPD	cross-product of the longest transverse diameter and perpendicular diameter
PR	partial response
QD	once daily
QW	once weekly
R-chemo	rituximab + chemotherapy
R-CHOP	rituximab, cyclophosphamide, doxorubicin, vincristine, prednisone
RNA	ribonucleic acid
SAE	serious adverse event
SARS-CoV-2	severe acute respiratory syndrome coronavirus 2
SCT	stem cell transplantation
SD	stable disease
SDi	shortest axis perpendicular to the longest transverse diameter
SoA	schedule of activity
SOP	standard operating procedure
SPD	sum of the product of the perpendicular diameters for multiple lesions
SUSARs	suspected unexpected serious adverse reaction
SUV _{max}	maximum standardized uptake value
TEAE	treatment-emergent adverse event
ULN	upper limit of normal
■	■

1. PROTOCOL SUMMARY

Protocol Title: A Phase 2, Multicenter, Open-Label Study of Parsaclisib, a PI3K δ Inhibitor, in Japanese Participants With Relapsed or Refractory Follicular Lymphoma (CITADEL-213)

Protocol Number: INCB 50465-213

Objectives and Endpoints:

Table 1 presents the primary and key secondary endpoints and objectives.

Table 1: Primary and Secondary Objectives and Endpoints

Objectives	Endpoints
Primary	
To assess the efficacy of parsaclisib in terms of ORR in participants with relapsed or refractory FL.	ORR, defined as the percentage of participants with a CR or PR as defined by revised response criteria for lymphomas (Cheson et al 2014), as determined by an IRC.
Key Secondary	
To assess CRR.	CRR, defined as the percentage of participants with a CR as defined by revised response criteria for lymphomas (Cheson et al 2014), as determined by an IRC.
To assess DOR.	DOR, defined as the time from first documented evidence of CR or PR until disease progression or death from any cause among participants who achieve an objective response, as determined by radiographic disease assessment provided by an IRC.
To assess PFS.	PFS, defined as the time from the date of the first dose of study treatment until the earliest date of disease progression, as determined by radiographic disease assessment provided by an IRC, or death from any cause.
To assess OS.	OS, defined as the time from the date of the first dose of study treatment until death from any cause.
To assess best percentage change in target lesion size.	Best percentage change in target lesion size from baseline, where target lesion size is measured by the sum of the product of the diameters of all target lesion sizes.
To characterize the safety and tolerability of parsaclisib.	Safety and tolerability assessed by monitoring the frequency and severity of AEs; includes performing physical examinations and collecting vital signs, 12-lead ECGs, and clinical laboratory data.

Overall Design:

Table 2 presents the key study design elements. Further study details are presented after the table.

Table 2: Key Study Design Elements

[figure not shown]
Study Phase	Phase 2
Clinical Indication	Relapsed or refractory FL
Population	Male and female Japanese participants at least 18 years of age who have relapsed or refractory FL (Grade 1, 2 or 3a) with disease progression after 2 or more prior systemic therapies
Number of Participants	Approximately 40 participants with history of 2 or more lines of treatment will be enrolled. Approximately 18 participants should have history of ASCT.
Study Design	
Single arm, open-label
 
Participants will receive parsacalisib 20 mg QD for 8 weeks followed by 2.5 mg QD. Participants will be evaluated for ORR by an IRC and followed for CRR, DOR, PFS, OS, and safety. Participants may receive treatment until disease progression, death, unacceptable toxicity, or consent withdrawal.
 
An interim futility analysis is planned when the first 20 participants have been evaluated for response or have been followed for at least 9 weeks or have permanently discontinued study treatment because of disease progression, withdrawal of consent, or death. Enrollment will continue during the interim futility analysis. The study will be terminated for futility if ≤ 7 of the 20 participants have responded (ie, CR or PR) based on assessments provided by the IRC; otherwise the study will continue. A timely assessment of response will be performed to avoid the risk of overenrollment.

Estimated Duration of Study Participation	Up to 28 days for screening, continuous treatment as long as participants are receiving benefit and have not met any criteria for study treatment withdrawal, 30 to 35 days for safety follow-up, and disease and survival follow-up until the end of the study. It is estimated that an individual will participate for an average of approximately 16 months, which includes each period mentioned above.
IDMC	Yes (external)

Treatment Groups and Duration:

This is a Phase 2, multicenter, open-label study evaluating parsacalisib treatment based on the primary endpoint of ORR. The study treatment will be administered orally. Participants may receive treatment until disease progression, death, HSCT (if become eligible) or unacceptable toxicity, or consent withdrawal.

Figure 1 presents the study design schema.

Figure 1: Study Design Schema

^aAn interim futility analysis is planned when the first 20 participants have been evaluated for response, have been followed for at least 9 weeks, or have permanently discontinued study treatment because of disease progression, withdrawal of consent, or death.

^bApproximately 18 participants with history of ASCT will be involved.

Adherence to the study design requirements, including those specified in the SoA, is essential and required for study conduct.

Table 3: Schedule of Activities

Procedure	Screening	Treatment			EOT	Follow-Up			Notes and Protocol Section
	Day -28 to -1	Day 1*	Every 4 Weeks Through Week 48 (± 3 Days)	Every 12 Weeks From Week 48 (± 1 Week)		Safety	Disease	Survival	
						EOT +30-35 Days		Every 12 Weeks (± 1 Week) after EOT	*All procedures are to be performed before administration of study treatment.
Informed consent	X								Section 8.1.1.
Contact IWRS	X	X	X	X	X				Section 8.1.3.
Inclusion & exclusion criteria	X	X							Section 5.1, Section 5.2.
Demography and medical history	X								Section 8.1.5.
Prior/concomitant medications	X	X	X	X	X	X			Section 6.6.
AE assessment	X	X	X	X	X	X			Section 8.3.1.
Comprehensive physical exam	X*				X				*Height required at screening only, Section 8.3.2.
Disease-specific physical exam		X	X	X		X			
Vital signs	X	X	X	X	X	X			Section 8.3.3.
12-lead ECG	X	X	X*	X*	X	X			*Week 4, Week 12, and every 12 weeks thereafter. Section 8.3.4.
ECOG status	X	X	X	X	X	X			Section 8.3.5.

Table 3: Schedule of Activities (Continued)

Procedure	Screening	Treatment		EOT	Follow-Up			Notes and Protocol Section
	Day -28 to -1	Day 1*	Every 4 Weeks Through Week 48 (± 3 Days)		Every 12 Weeks From Week 48 (± 1 Week)	Safety	Disease	
CT/MRI scan	X		Every 8 weeks through Week 24 (± 1 week), then every 12 weeks through Week 96, and then every 24 weeks thereafter until PD.				X*	*All procedures are to be performed before administration of study treatment. *Only for participants who discontinue study treatment for reasons other than disease progression. Will continue to be performed per assessment schedule (every 8, 12, 24 weeks as appropriate) until disease progression, start of new anti-lymphoma therapy, withdrawal of consent, end of the study, or death, whichever occurs first. Section 8.2.1.
Bone marrow exam	X		X*	X*			X*	Required at baseline except if participant had a bone marrow exam per standard of care within ~60 days of first dose or had a previous exam after the last therapy. *If disease is present in bone marrow at baseline, a bone marrow biopsy is required to confirm CR. Section 8.2.2.
FDG-PET	X							Only for participants who submit earlier archived lymph nodes or tissue biopsies instead of newly obtained samples after the previous therapy. If FDG-PET assessment was performed as standard of care before signing of the ICF, but within 28 days of Day 1, then the results from that assessment can be used.
PJP prophylaxis		X						PJP prophylaxis will continue for 2 to 6 months after the last dose of study treatment. Section 6.6.1.

Table 3: Schedule of Activities (Continued)

Procedure	Screening	Treatment			EOT	Follow-Up			Notes and Protocol Section
	Day -28 to -1	Day 1*	Every 4 Weeks Through Week 48 (± 3 Days)	Every 12 Weeks From Week 48 (± 1 Week)		Safety	Disease	Survival	
						EOT +30-35 Days		Every 12 Weeks (± 1 Week) after EOT	*All procedures are to be performed before administration of study treatment.
Study drug dispensing		X	X	X					Section 8.1.3.
Study drug compliance		X	X	X	X				Section 6.4.
Study drug administration at site		X	X						██████████ Day 1, Week 4, and Week 12. Section 8.4.
Disease follow-up							X		Only for participants who discontinue study treatment for reasons other than disease progression. Section 8.8.2.
Survival follow-up								X	May be conducted by phone or email. Section 8.8.3.

Table 4: Schedule of Laboratory Assessments

Laboratory Tests	Screening	Treatment				EOT	Safety Follow-Up	Notes and Protocol Section
	Day -28 to -1	Day 1	Week 2 and Week 6 (± 3 Days)	Every 4 Weeks Through Week 48 (± 3 Days), (Week 4 included)	Every 12 Weeks From Week 48 (± 1 Week)		EOT + 30-35 Days	
Serum chemistries	X	X*		X	X	X	X	*Day 1 assessments may be omitted if the screening tests occurred in the preceding 7 days. If needed, Day 1 blood draws should be performed before administration of study treatment. Section 8.3.6.1.
Hematology	X	X*	X	X	X	X	X	
Serology	X			X*	X*	X*		*Samples for CMV DNA analysis only. Section 8.3.6.3.
Serum pregnancy	X					X	X	Only for females of childbearing potential; negative pregnancy test must be obtained within 14 days before administration of study treatment. Section 8.3.6.2.
Urine pregnancy				X	X			
HIV testing	X							Section 8.3.6.

Table 4: Schedule of Laboratory Assessments (Continued)

Laboratory Tests	Screening	Treatment				EOT	Safety Follow-Up	Notes and Protocol Section
	Day -28 to -1	Day 1	Week 2 and Week 6 (± 3 Days)	Every 4 Weeks Through Week 48 (± 3 Days), (Week 4 included)	Every 12 Weeks From Week 48 (± 1 Week)		EOT + 30-35 Days	
Tumor biopsy	X			X*		X*	
Participants must be willing to undergo an incisional, excisional or core needle lymph node or tissue biopsy or provide a lymph node or tissue biopsy after completion of the last therapy.
 
*An optional biopsy at Week 4 and is encouraged. A lymph node or tissue biopsy is strongly encouraged at time of progression OR at time of relapse following response of PR or better.
 
Tumor biopsy is not mandatory for participants who submit earlier archived lymph nodes or tissue biopsies.
 
Section 8.5.3.
	

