3. OBJECTIVES AND ENDPOINTS

Table 5 presents the objectives and endpoints.

Table 5: Objectives and Endpoints

Objectives	Endpoints
Primary	
To assess the efficacy of parsaclisib in terms of ORR in participants with relapsed or refractory FL.	ORR, defined as the percentage of participants with a CR or PR as defined by revised response criteria for lymphomas (Cheson et al 2014), as determined by an IRC.
Secondary	
To assess CRR.	CRR, defined as the percentage of participants with a CR as defined by revised response criteria for lymphomas (Cheson et al 2014), as determined by an IRC.
To assess DOR.	DOR, defined as the time from first documented evidence of CR or PR until disease progression or death from any cause among participants who achieve an objective response, as determined by radiographic disease assessment provided by an IRC.
To assess PFS.	PFS, defined as the time from the date of the first dose of study treatment until the earliest date of disease progression, as determined by radiographic disease assessment provided by an IRC, or death from any cause.
To assess OS.	OS, defined as the time from the date of the first dose of study treatment until death from any cause.
To assess best percentage change in target lesion size.	Best percentage change in target lesion size from baseline, where target lesion size is measured by the sum of the product of the diameters of all target lesion sizes.
To characterize the safety and tolerability of parsaclisib.	Safety and tolerability assessed by monitoring the frequency and severity of AEs; includes performing physical examinations and collecting vital signs, 12-lead ECGs, and clinical laboratory data.

Table 5: Objectives and Endpoints (Continued)

Objectives	Endpoints
[Redacted content]	

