7.1.1. Reasons for Discontinuation

Participants **must** be discontinued from study treatment for the following reasons:

- The participant has died.
- The participant has experienced an unacceptable toxicity defined as follows:
 - Occurrence of an AE that is related to study treatment that, in the judgment of the investigator or the sponsor's medical monitor, compromises the participant's ability to continue study-specific procedures or is considered to not be in the participant's best interest.
 - Persistent AE requiring a delay of therapy for more than 2 weeks (14 days) unless a greater delay has been approved by the sponsor.
- The participant is unable to tolerate study treatment.
- The participant has an objective radiographic tumor response of PD/PMD.
- Further participation would be injurious to the participant's health or well-being, in the investigator's medical judgment.
- The participant becomes pregnant.
- Informed consent is withdrawn. *Note:* Consent withdrawn means that the participant can no longer be followed. Participants may choose to discontinue study treatment and remain in the study to be followed for disease progression and survival per the schedule of assessments.
- The participant is considered lost-to-follow-up when they repeatedly fail to return for scheduled visits and is unable to be contacted by the study site (eg, after 3 telephone calls and/or a certified letter or local equivalent).
- The study is terminated by the sponsor.
- The study is terminated by the local health authority, IRB, or IEC.

Participants **may** be discontinued from study treatment in the following situation:

- If a participant is noncompliant with study procedures or study treatment administration in the investigator's opinion, then the sponsor should be consulted for instruction on handling the participant.

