8.2. Efficacy Assessments

8.2.1. Computed Tomography Scan or Magnetic Resonance Imaging

Participants will undergo a diagnostic-quality CT or MRI to evaluate measurable disease. If CT is not available, is not practicable, or is contraindicated, then an MRI may be substituted. Every effort must be made to use the same modality for disease assessment throughout the study for each individual participant. Lesion assessment must be done for the neck, chest, abdomen, and pelvis.

If CT/MRI assessment was performed as standard of care before signing of the ICF but within 28 days of Day 1, then the results from that assessment must be recorded in the eCRF if used in lieu of a study-specific assessment.

The disease assessment schedule also applies to those participants who discontinue study treatment for reasons other than disease progression until disease progression, start of new anticancer therapy, withdrawal of consent, end of the study, or death, whichever occurs first. Imaging should not be delayed for interruption of study treatment.

No further CT/MRI is required as per Protocol-defined timepoint after all study participants have completed at least 12 months of study participation (starting from the first dose of study treatment).

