8.8.2. Post-Treatment Disease Follow-Up

Participants who discontinue study treatment for a reason other than disease progression will continue to be followed for disease assessments by radiologic imaging [REDACTED] per the schedule of assessments (see timepoints for CT/MRI [REDACTED] in [Table 3](#). Every effort should be made to collect information regarding disease status until any 1 of the following occurs:

- The start of new antineoplastic therapy.
- Disease progression.
- Consent withdrawal
- Death.
- The end of the study.

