**Table 2: Evaluation and Censoring of Progression-Free Survival**

Situation	Outcome	Date of Progression or Censoring
No baseline tumor assessments	Censored	Day 1
No valid postbaseline response assessments	Censored	Day 1
Progression documented between scheduled response assessments	Progressed	Date of first overall response of PD
No progression	Censored	Date of last valid radiologic assessment (not NE and not missing)
Study discontinuation for undocumented progression	Censored	Date of last valid radiologic assessment (not NE and not missing)
Study discontinuation for toxicity or other reason	Censored	Date of last valid radiologic assessment (not NE and not missing)
New anticancer treatment started	Censored	Date of last valid radiologic assessment (not NE and not missing) on/before starting a new anticancer treatment
Death before first progressive response assessment	Progressed	Date of death
Death between adequate response assessments	Progressed	Date of death
Death or progression after two or more missed assessments	Censored	Date of last valid radiologic assessment (not NE and not missing) before the missed assessments

NE = not evaluable.

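### IRC-read PFS and DOR are probably censored informatively when the site calls progression and the IRC does not, and no planned analysis tests the IRC estimate for this

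*Protocol*

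**What the plan says.** - **Endpoint.** Protocol Section 3 dates PFS to progression "as determined by radiographic disease assessment provided by an IRC, or death from any cause". DOR progression is also read by the IRC. Under SAP 7.4.2 and 7.4.3 the IRC's clinical reviewer supplies the progression date.
- **Local reading.** SAP 7.2 has sites apply the same CT-based Lugano criteria at every assessment and record the result in the eCRF.
- **End of treatment.** Protocol 7.1.1 makes discontinuation mandatory when "The participant has an objective radiographic tumor response of PD/PMD". It names no reader.
- **End of scanning.** The CT/MRI row of Protocol Table 3 runs scans every 8 weeks to Week 24, "then every 12 weeks through Week 96, and then every 24 weeks thereafter until PD". Its note limits post-treatment scans: "Only for participants who discontinue study treatment for reasons other than disease progression". Protocol 8.2.1 and 8.8.2 carry the same limit.
- **Censoring.** In SAP Table 2, a participant without progression is censored at the last valid radiologic assessment. One who starts a new anticancer treatment is censored at the last valid assessment on or before that start. SAP 7.4.2 applies the same algorithm to DOR.
- **Sensitivity analyses.** The only one named for an IRC endpoint is an optional analysis of ORR (SAP 7.3.1). Investigator-read PFS and DOR are planned separately (SAP 7.5.2).

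**The concern.** Two readers are involved, and one reader's call appears to end the other's data. If the site reads progression and the IRC does not, treatment ends for progression, so the participant falls outside the group that continues to be scanned. The IRC then has no later protocol scan on which to call progression, and the participant leaves the IRC risk set as censored.

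Kaplan-Meier estimation assumes that censored participants have the same prospects as those who remain at risk. A participant whose site has just read progression on the same criteria probably has worse prospects. Protocol 2.2.1 justifies the IRC by observer bias and variability, so the plan itself expects readers to differ.

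The trial has one arm and about 40 participants. IRC PFS and DOR will be read as absolute figures, with no control arm to share the bias.

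**Working it through.** **1. Plan's own figures.** The documents give no PFS or DOR assumption and no discordance rate, so there is no stated figure to reproduce on this point. The ORR figures do reproduce. At least 21 of 40 responders are needed (exact lower limit 36.1%; 20 of 40 gives 33.8%), with probability 91.8% at a true ORR of 62%, against a stated figure of approximately 90%. Stopping with 7 or fewer of 20 has probability 60.10% at 35% and 1.32% at 62%, as stated. None of these depends on progression censoring.

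**2. Tracing one participant.** The site reads PD at scan k and the IRC reads no PD at scan k.
- Treatment ends for progression (Protocol 7.1.1).
- No further protocol scan is due (Protocol Table 3, 8.2.1, 8.8.2).
- The IRC has no progression date, so SAP Table 2 censors at the last valid scan, normally scan k, under its no-progression row or its new-treatment row.
- A later death counts as an event only if neither the new-treatment row nor the row for two or more missed assessments applies first. The SAP does not say whether scans that the protocol no longer requires count as missed.

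**3. Illustration of size.** These assumptions are not in the documents:
- exponential time to IRC progression with median m of 12, 18 or 24 months;
- a share d of participants, 10% to 40%, whose site calls PD one or three scheduled scans before the IRC would;
- scans at Weeks 8, 16 and 24, then every 12 weeks to Week 96;
- no deaths or dropout;
- 60,000 simulated participants per scenario.

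The last scan before month 12 is Week 48, which is 48/4.348 = 11.04 months. For m = 12, survival there is 2^(-11.04/12) = 0.528, which the simulation matches (52.7% to 53.0%).

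12-month IRC PFS (%), with differences from continued scanning in points:

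| m (months) | d | Lag (scans) | Scans continue | Censored at site PD | Rise | Site PD as event | Fall |
|---|---|---|---|---|---|---|---|
| 12 | 10% | 1 | 52.8 | 55.4 | 2.6 | 52.1 | 0.7 |
| 12 | 10% | 3 | 52.7 | 53.6 | 0.9 | 50.6 | 2.1 |
| 12 | 20% | 1 | 52.9 | 58.5 | 5.6 | 51.4 | 1.5 |
| 12 | 20% | 3 | 52.9 | 54.9 | 2.0 | 48.8 | 4.1 |
| 12 | 40% | 1 | 52.8 | 64.7 | 11.9 | 49.7 | 3.1 |
| 12 | 40% | 3 | 52.9 | 57.4 | 4.5 | 45.0 | 7.9 |
| 18 | 20% | 1 | 65.2 | 69.8 | 4.6 | 64.0 | 1.2 |
| 18 | 20% | 3 | 65.0 | 67.0 | 2.0 | 61.4 | 3.6 |
| 24 | 20% | 1 | 72.8 | 76.7 | 3.9 | 71.7 | 1.1 |
| 24 | 20% | 3 | 72.4 | 74.1 | 1.7 | 69.3 | 3.1 |

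Across all scenarios run, the rise is 0.9 to 11.9 points; at d = 20% it is 1.7 to 5.6. Counting site PD as an event falls about 1 to 8 points below continued scanning, so in these scenarios the two analyses bracket the target.

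**4. Null case.** With 20% of participants given site calls unrelated to true progression, 12-month PFS does not move: 52.9% and 52.9% for m = 12, 65.6% and 65.6% for m = 18, 72.4% and 72.4% for m = 24.

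**5. Medians.** Simulated medians move only in scan-date steps. For m = 12 and d = 20%, the median goes from 13.8 months (Week 60) to 16.6 (Week 72) at a lag of one scan and does not move at three. At d = 10% it does not move at either lag.

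**The case against.** **The stop rule names no reader.** Protocol Table 3, 7.1.1, 8.2.1 and 8.8.2 refer only to PD or disease progression. Protocol 8.8.3 speaks of confirmed progression without saying who confirms it. The charter that governs independent review is not available and could contain a confirmation step. This stands: that the site's call is decisive is an inference from local reading and from the absence of any stated IRC step.

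**Censoring is not complete.** A death can still count as an event, and SAP 7.2 lets the IRC's clinical reviewer use clinical as well as radiographic data. This stands and would reduce the effect.

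**The plan already shows the discordance.** Investigator-read PFS and DOR count these calls as events (SAP Appendix A, Tables 2.2.2 and 2.2.4), and Listings 2.6.1 to 2.6.3 and 2.6.7 give both readings by participant. A reader might infer that nothing in the plan bears on the problem; that would be wrong. But the investigator analysis replaces the IRC reading for every participant. It mixes general reader differences with the censoring effect and does not test the IRC estimate.

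**The consequence is limited.** PFS and DOR are secondary, with no formal test and no threshold. At N = 40 and 12-month PFS of 0.528, ignoring censoring, sampling error alone is about 1.96 x sqrt(0.528 x 0.472/40) = 0.155, or roughly 15 points either way. This stands as to priority. Sampling error does not excuse a bias with a likely direction, and the check is cheap.

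**Conclusion.** The point holds in a limited form. As written, treatment and protocol scans appear to stop at site-read progression. An unconfirmed call then leads to IRC censoring that is probably informative and likely biases IRC PFS and DOR upward. Under the assumptions above, 12-month IRC PFS rises by about 1 to 12 points, about 2 to 6 at 20% discordance, and about 0 if the calls are unrelated to true progression. The DOR mechanism is the same, but its size has not been computed. ORR and the futility rule are unaffected.

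Three stronger readings are tempting but not supported:
- **That the bias is certain.** The null case shows none, and the reader who triggers the stop is inferred.
- **That the size is larger.** Removing a share d of true progressions at the scan where they occur gives S^(1-d): 0.528 becomes 0.563, 0.600 or 0.640 at d = 10%, 20% or 30%, a rise of 3.5, 7.2 or 11.2 points. This treats every unconfirmed site call as true progression at that scan. The proper comparator for an IRC endpoint is the IRC date had scanning continued.
- **That the SAP Table 2 row "Study discontinuation for undocumented progression" is the main route.** That row concerns leaving the study. A participant with site-called progression stops treatment and moves to survival follow-up (Protocol 7.1 and 8.8.3), so the no-progression and new-treatment rows are the ones that normally apply.

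**What to change.** Add to SAP 7.4.2 and 7.4.3 one prespecified sensitivity analysis of IRC PFS and DOR. It should count investigator-called PD not confirmed by the IRC as an event at the date of that assessment, and otherwise leave SAP Table 2 unchanged. Describe it as a conservative bound, because it can fall below the value that continued scanning would give.

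Report it beside the primary IRC analysis, with:
- a count of site-versus-IRC discordance on progression;
- the number censored for new therapy;
- the number censored for undocumented progression.

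Do not count every new-therapy start as an event in this analysis. The SAP bases its censoring on named FDA guidance (7.4.3), and SAP Section 3 allows treatment to end for HSCT. If transplant were classed as new therapy, which the documents do not settle, a responder going to transplant could be counted as progressed.

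The cost is one extra analysis and a short table on data already collected, with no extra scans. The downside is a second, lower PFS and DOR figure to report and explain.

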8.2.2. Bone Marrow Examination

Bone marrow examination is required as a baseline assessment except in the following circumstances:

- Participant had a bone marrow examination performed as per standard of care within approximately 60 days from the first dose of study treatment.
- Participant had a bone marrow examination performed after the last treatment for NHL and the results showed lymphoma involvement of the bone marrow.

Subsequently, bone marrow examination will be performed and the sample(s) sent to a local histopathology laboratory to confirm CR, or as clinically indicated. If the bone marrow does not have lymphoma involvement at baseline, a repeat marrow examination is not required to confirm indication of CR on imaging.

All bone marrow examinations should include a unilateral aspiration and biopsy, when feasible.

The pathology report result from the bone marrow examination will be captured in the eCRF.

Note: Bone marrow biopsies and aspirates collected at screening should be evaluated locally. These materials are not to be sent to the central laboratory or the sponsor.

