APPENDIX D. LUGANO CLASSIFICATION FOR RESPONSE ASSESSMENT (CT-BASED ONLY)

Site	CT-Based Response
	Complete radiologic response (all of the following)
Lymph nodes and extralymphatic sites	Target nodes/nodal masses must regress to ≤ 1.5 cm in LDi.
Nonmeasured lesion	Absent.
Organ enlargement	Regress to normal.
New lesions	None.
Bone marrow	Normal by morphology; if indeterminate, immunohistochemistry negative.
	Partial remission (all of the following)
Lymph nodes and extralymphatic sites	
 • $\geq 50\%$ decrease in SPD of up to 6 target measurable nodes and extranodal sites. • When a lesion is too small to measure on CT, assign 5 mm \times 5 mm as the default. • When no longer visible, 0 \times 0 mm. For a node > 5 mm \times 5 mm but smaller than normal, use actual measurement.
Nonmeasured lesions	Absent/regressed, but no increase.
Organ enlargement	Spleen must have regressed by $> 50\%$ in length beyond normal.
New lesions	None.
Bone marrow	Not applicable.
	Stable disease
Target nodes/nodal masses, extranodal lesions	$< 50\%$ decrease from baseline in SPD of up to 6 dominant, measurable nodes and extranodal sites; no criteria for PD are met.
Nonmeasured lesions	No increase consistent with progression.
Organ enlargement	No increase consistent with progression.
New lesions	None.
Bone marrow	Not applicable.

Site	CT-Based Response
	Progressive disease (requires at least 1 of the following)

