#### 4.1.2. Study Day

If a visit/reporting date is on or after Day 1, then the study day at the visit/reporting date will be calculated as

$$\text{Day \#} = (\text{Visit/Reporting Date} - \text{Day 1 date} + 1).$$

If the visit/reporting date is before Day 1, then the study day at the visit/reporting date will be calculated as

$$\text{Day \#} = (\text{Visit/Reporting Date} - \text{Day 1 date}).$$

A study day of -1 indicates 1 day before Day 1.

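### Table 3 and Section 8.2.2 of the protocol waive the baseline bone marrow exam under different rules, so some complete responses could rest on an old negative marrow

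*Protocol*

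**What the plan says.** **Protocol Table 3 (Schedule of Activities), bone marrow row.** A baseline exam is required unless the participant had a standard-of-care exam "within ~60 days of first dose or had a previous exam after the last therapy". The note adds: "If disease is present in bone marrow at baseline, a bone marrow biopsy is required to confirm CR." It then cites Section 8.2.2. The text before the table says: "Adherence to the study design requirements, including those specified in the SoA, is essential and required for study conduct."

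**Protocol Section 8.2.2.** There are two exceptions to the baseline exam. The first is: "Participant had a bone marrow examination performed as per standard of care within approximately 60 days from the first dose of study treatment." The second is: "Participant had a bone marrow examination performed after the last treatment for NHL and the results showed lymphoma involvement of the bone marrow." The section then provides for on-study marrow exams to confirm CR or when clinically indicated, with this relief: "If the bone marrow does not have lymphoma involvement at baseline, a repeat marrow examination is not required to confirm indication of CR on imaging."

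**Protocol Appendix D.** The marrow criterion for CR is "Normal by morphology; if indeterminate, immunohistochemistry negative". For partial response (PR), marrow is listed as not applicable. For progressive disease, the list includes marrow involvement that is new or has come back.

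**SAP.** Section 7.2 takes its exceptions to the baseline exam from protocol Section 8.2.2 and repeats the relief from a second marrow when the baseline marrow is clear. Section 4.1.3 defines baseline as the last nonmissing value before first dose, with no age limit. Section 7.4.1 bases CRR on the best overall response given by the clinical reviewer of the independent review committee (IRC). Section 7.3.2 has a subgroup by baseline marrow involvement.

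**The concern.** The Table 3 note lacks the condition that the post-therapy exam must have shown involvement. That changes what a site must do. A site working from Table 3 can skip an exam that Section 8.2.2 requires, while the SAP assumes that the Section 8.2.2 rule was applied.

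The missing exam matters because the baseline marrow result decides whether the marrow is examined again at CR. All participants have relapsed or refractory disease (inclusion criterion 3), so a negative exam done after the last therapy may predate the current relapse. If that result serves as baseline, a CR on imaging can be accepted with no recent evidence on the marrow. At stake are mainly CRR, the split between CR and PR, and the baseline marrow subgroup.

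**Working it through.** The plan gives no figure on this point to reproduce. The check has four steps.

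**1. The two waiver rules as logical conditions.** Let A = standard-of-care exam within about 60 days of first dose, B = exam after the last therapy, C = an exam under B showed marrow involvement. Exams inside the window are taken to be standard-of-care exams.

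- Table 3 waives if A or B.
- Section 8.2.2 waives if A or (B and C).

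| Case | Table 3 | Section 8.2.2 |
|---|---|---|
| A true | waived | waived |
| A false, B false | exam required | exam required |
| A false, B true, C true | waived | waived |
| A false, B true, C false | waived | exam required |

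The rules differ only in the last row: every exam after the last therapy is older than about 60 days and none showed involvement.

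**2. From the last row to CR.** Under Table 3 there is no new baseline exam. If the old negative is taken as the baseline result (SAP 4.1.3 sets no age limit that would prevent this), the no-repeat rule in Section 8.2.2 and SAP 7.2 applies. A CT-based CR then needs no marrow, while Appendix D still asks for a normal one. Neither document says whether an exam outside the Section 8.2.2 exceptions counts as baseline for that rule.

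**3. Which endpoints can move.**

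- *CRR, the CR/PR split and the marrow subgroup:* directly, through step 2.
- *Objective response rate (ORR):* a CT-based CR that is not accepted as CR would ordinarily still be a PR, because marrow does not enter the PR criteria. By this route ORR is essentially unchanged.
- *Progression-free survival (PFS), duration of response (DOR) and, rarely, ORR:* a positive marrow found on study could be read against an old negative baseline as new involvement, hence progression. ORR could be reached only if this happened by the time of the first response.

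**4. Size for CRR.** Input from the protocol: N = 40 (Section 10.1). The CR counts 4, 8, 12 and 20 are assumptions; the documents give none.

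- Shift in the estimate per affected CR: 1/40 = 2.5 percentage points.
- Exact (Clopper-Pearson) 95% lower limit for x CRs: L(x) = 2.5th percentile of Beta(x, 40 − x + 1).

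| Assumed CRs | L(x) | L(x − 1) | Fall in lower limit |
|---|---|---|---|
| 4 | 2.793% | 1.574% | 1.2 points |
| 8 | 9.052% | 7.338% | 1.7 points |
| 12 | 16.563% | 14.601% | 2.0 points |
| 20 | 33.802% | 31.512% | 2.3 points |

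These rows show the effect of not counting one CR. They are illustrations, not bounds: the fall depends on the CR count and on how many CRs are affected.

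**The case against.** The best case for the plan is that the Table 3 note merely abbreviates Section 8.2.2. The row cites that section, SAP 7.2 takes its exceptions from there alone, and three of the four cases agree. The analysis plan therefore has no internal conflict about the waiver. This stands as far as it goes, and it keeps the point small. It does not remove it: the omitted condition changes what a site must do, the protocol makes the schedule binding in its own right, and no text says which passage prevails.

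A second objection is that the consequence for CR is conditional. Section 8.2.2 starts from a marrow exam to confirm CR. The relief from it depends on the old result counting as baseline, and the IRC also reviews clinical data under a charter that is not available here. This stands in full.

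Three stronger readings are tempting, and the documents do not support them.

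- *CRR is biased upward.* It could be, but only if affected participants exist, the old negative is taken as baseline and the charter lets such CRs stand. The marrow may also have been truly normal.
- *Any CR without an on-study marrow is suspect.* Section 8.2.2 itself lets a negative exam up to about 60 days old stand without a repeat at CR. The conflict concerns only older negatives.
- *The primary endpoint is compromised.* Marrow is not applicable for PR, so the main route leaves ORR alone. The opposite absolute, that nothing but CRR can move, is not supported either, because of the marrow criterion for progression.

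**Conclusion.** The point holds as a minor one. The two passages set different waiver rules, and they differ only for participants whose marrow exams after the last therapy all showed no involvement and are all older than about 60 days.

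The main possible effect is an upward bias in CRR, with matching changes in the CR/PR split and the marrow subgroup. A smaller effect on PFS and DOR, and rarely on ORR, is possible through the progression criterion. The sample-size statement in protocol Section 10.1 concerns ORR and does not depend on this point.

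The size cannot be computed from the documents. It is 2.5 points of CRR per affected CR at N = 40, and the number affected may be zero. The conclusion on bias assumes that a site followed Table 3, that the old negative was used as baseline, and that the IRC did not ask for a recent marrow.

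**What to change.** **Protocol.** Reconcile the Table 3 note and Section 8.2.2 so that both state one waiver rule. This review does not say which rule is right; SAP 7.2 already refers to Section 8.2.2.

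**SAP, flag.** Add a flag for participants who had one or more pre-dose marrow exams after the last therapy, none of which showed involvement and all of which fall outside the window of about 60 days. The SAP has no 60-day wording of its own, so state the programming cutoff and any tolerance. The study-day convention in SAP 4.1.2 ("A study day of -1 indicates 1 day before Day 1") can be used: study day -60 is then 60 days before Day 1. Report the number flagged.

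**SAP, sensitivity line.** If the number is not zero, add to Section 7.4.1 one descriptive CRR line that does not count CRs in flagged participants without an on-study marrow. Keep the IRC best overall response for the main CRR analysis. The marrow subgroup in Section 7.3.2 needs no recoding.

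**Cost.** One wording change, one flag from marrow dates and results that SAP 7.5.2 already lists, and a sensitivity CRR that may be slightly lower than the main one. Depending on the reconciliation, some later participants might need a baseline exam that Section 8.2.2 already requires. If enrollment is complete, only the SAP steps have an effect.
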